15.6 Sample Size

Up to 20 CF Care Centers are eligible for enrollment. Sample size will be determined based on CO-RDP WGS finding of highly related NTM species and subspecies among patients receiving care at an individual CF Care Center.

16 DATA COLLECTION, RETENTION AND CLINICAL MONITORING

16.1 Data Collection Instruments

Study personnel at each site will enter data from the electronic medical record and CF Registry corresponding to a participant's visit into the protocol-specific electronic REDCap database when the information corresponding to that visit is available. Participants will not be identified by name in the study database to be collected by the Sponsor (or designee), but will be identified by a site number, participant number and initials.

For all REDCap data collection, the time and date stamp tracks the person entering or updating data and creates an electronic audit trail.

The Investigator is responsible for all information collected on participants enrolled in this study. All data collected during the course of this study must be reviewed and verified for completeness and accuracy by the Investigator. At the completion of the study, a copy of the REDCap data will be provided to the site to be retained at the Investigator's site.

The data may be monitored by the CFF at any time during the study.

16.2 Data Management Procedures

The National Jewish Health Research Informatics Services Core will be used as a central location for data processing and management. REDCap, a software toolset and workflow methodology for electronic collection and management of research and clinical trial data, was developed by Vanderbilt University, with collaboration from a consortium of institutional partners. REDCap data collection projects rely on a thorough study-specific data dictionary defined in an iterative self-documenting process by all members of the research team with planning assistance from the Research Informatics Services Core. The iterative development and testing process results in a well-planned data collection strategy for individual studies. REDCap servers are housed in a local data center at National Jewish Health and all web-based information transmission is encrypted. REDCap was developed specifically around HIPAA-security guidelines and is recommended to National Jewish Health researchers by both our Privacy Office and Institutional Review Board. REDCap currently supports 240+ academic/non-profit consortium partners on six continents and over 26,000 research end-users (www.project-redcap.org).

Data Quality Control and Reporting

After data have been entered into the study database, data validation checks will be applied on a regular basis. As part of data analysis, [name], the lead biostatistician on the study, will monitor for data outliers and will perform data control. If data entry errors are encountered, the

study database will be updated in accordance with the resolved queries. All changes to the study database will be documented in an audit trail.

163 Security and Archival of Data

REDCap is a secure, web-based application designed to support data capture for research studies. REDCap is maintained by the REDCap Consortium which is comprised of over 3,500 institutional partners including National Jewish Health, and is administrated locally by the National Jewish Health Research Informatics Services.

REDCap utilizes a suite of features that support HIPAA compliance. Access to the database requires user authentication with password. Data is accessed based on the individual's role on the project. Logging and audit trails are maintained on all data interactions. All data is stored on a secure server, and backups are encrypted. Automatic backup of the servers are performed twice daily.

164 Availability and Retention of Investigational Records

The Investigator must make study data accessible to the monitor, other authorized representatives of the Sponsor (or designee), IRB/IEC, and Regulatory Agency (e.g., FDA) inspectors upon request. Hard copy files will not be created.

All study information will be maintained in REDCap for a period of 5 years after database lock. There may be other circumstances for which the Sponsor is required to maintain study records and, therefore, the Sponsor should be contacted prior to removing study records for any reason.

165 Monitoring

The study PIs and the CFF are authorized to monitor the study. By signing this protocol, the Investigator grants permission to the Sponsor (or designee), and appropriate regulatory authorities to conduct on-site monitoring and/or auditing of all appropriate study documentation. Monitoring visits will be conducted by representatives of the Sponsor according to the U.S. CFR 21 Part 312 and ICH Guidelines for GCP (E6) and to ensure investigator compliance to 21 CFR Parts 50, 56 and 312 and to GCP.

166 Participant Confidentiality

In order to maintain participant confidentiality, only a site number, participant number and participant initials will identify all study participants in REDCap. The participant's CFF patient registry number will also be collected. Additional participant confidentiality issues (if applicable) are covered in the Clinical Study Agreement.

17 ADMINISTRATIVE, ETHICAL, REGULATORY CONSIDERATIONS

The study will be conducted according to the Declaration of Helsinki, Protection of Human Volunteers (21 CFR 50), Institutional Review Boards (21 CFR 56), and Obligations of Clinical Investigators (21 CFR 312).

To maintain confidentiality, all laboratory specimens, evaluation forms, reports and other records will be identified by a coded number and initials only. Clinical information will not be released without written permission of the participant, except as necessary for monitoring by the FDA.

The Investigator must also comply with all applicable privacy regulations (e.g., Health Insurance Portability and Accountability Act of 1996, EU Data Protection Directive 95/46/EC).

17.1 Protocol Amendments

Any amendment to the protocol will be written by the Sponsor. Protocol amendments cannot be implemented without prior written IRB/IEC approval except as necessary to eliminate immediate safety hazards to participants. A protocol amendment intended to eliminate an apparent immediate hazard to participants may be implemented immediately, provided the IRBs are notified within 5 working days.

17.2 Institutional Review Boards and Independent Ethics Committees

The protocol and consent form will be reviewed and approved by the IRB/IEC of each participating center prior to study initiation. Serious adverse experiences regardless of causality will be reported to the IRB/IEC in accordance with the standard operating procedures and policies of the IRB/IEC, and the Investigator will keep the IRB/IEC informed as to the progress of the study. The Investigator will obtain assurance of IRB/IEC compliance with regulations.

Any documents that the IRB/IEC may need to fulfill its responsibilities (such as protocol, protocol amendments, Investigator's Brochure, consent forms, information concerning participant recruitment, payment or compensation procedures, or other pertinent information) will be submitted to the IRB/IEC. The IRB/IECs written unconditional approval of the study protocol and the informed consent form will be in the possession of the Investigator before the study is initiated. The IRB/IEC's unconditional approval statement will be transmitted by the Investigator to the Sponsor or designee prior to the shipment of study supplies to the site. This approval must refer to the study by exact protocol title and number and should identify the documents reviewed and the date of review.

Protocol and/or informed consent modifications or changes may not be initiated without prior written IRB/IEC approval except when necessary to eliminate immediate hazards to the participants or when the change(s) involves only logistical or administrative aspects of the study. Such modifications will be submitted to the IRB/IEC and written verification that the modification was submitted and subsequently approved should be obtained.

The IRB/IEC must be informed of revisions to other documents originally submitted for review; serious and/or unexpected adverse experiences occurring during the study in accordance with the standard operating procedures and policies of the IRB; new information that may affect adversely the safety of the participants of the conduct of the study; an annual update and/or request for re-approval; and when the study has been completed.

17.3 Informed Consent Form

N/A

17.4 Consent for Collection and Use of CFF Registry ID Number

To facilitate possible future evaluation of retrospective and prospective information from all participants in this study, the participant's CFF Registry ID number will be collected. The CFF registry collects data on all CF patients who consented to participate in the CFF registry and who are followed at CFF-accredited care centers. The registry data includes information from clinical

encounters, hospitalizations courses of antibiotics, and year-end surveys. Data also include microbiology results, spirometry results, CF genotype and other information. If specific consent is given to collect this number, the participant's CF registry number will be recorded in the CRF.

175 Publications

The preparation and submittal for publication of manuscripts containing the study results shall be in accordance with a process determined by mutual written agreement among the study Sponsor and participating institutions. The publication or presentation of any study results shall comply with all applicable privacy laws, including, but not limited to, the Health Insurance Portability and Accountability Act of 1996.

176 Investigator Responsibilities

By signing the Agreement of Investigator form, the Investigator agrees to:

1. Conduct the study in accordance with the protocol and only make changes after notifying the Sponsor (or designee), except when to protect the safety, rights or welfare of participants.
2. Personally conduct or supervise the study (or investigation).
3. Ensure that the requirements relating to obtaining informed consent and IRB review and approval meet federal guidelines, as stated in § 21 CFR, parts 50 and 56.
4. Ensure that all associates, colleagues and employees assisting in the conduct of the study are informed about their obligations in meeting the above commitments.
5. Maintain adequate and accurate records in accordance with §21 CFR 312.62 and to make those records available for inspection with the Sponsor (or designee).
6. Ensure that an IRB that complies with the requirements of §21 CFR part 56 will be responsible for initial and continuing review and approval of the clinical study.
7. Promptly report to the IRB and the Sponsor (or designee) all changes in the research activity and all unanticipated problems involving risks to participants or others (to include amendments and IND safety reports).
8. Seek IRB approval before any changes are made in the research study, except when necessary to eliminate hazards to the participants.
9. Comply with all other requirements regarding the obligations of clinical investigators and all other pertinent requirements listed in § 21 CFR part 312.

APPENDIX 2 REDCAP USER GUIDE

So, you've received a letter from National Jewish Health Advanced Diagnostic Laboratories (NJH ADx) saying you have patients at your center with a highly similar strain of NTM. Now what?

1. Contact [name] at NJH. She will help you with initial questions regarding study design and study start-up, including IRB and database requirements.
2. For NJH REDCap access, you will be sent a link to complete REDCap training. You will be asked the following:
 - For the question "Are you an employee of National Jewish Health?" select No.
 - Explain your affiliation as "HALT NTM"
 - National Jewish Health Sponsor is "[name]"
 - For department, indicate your CF center/institution name.
 - Complete the rest as indicated.
 - Email [name] or [name] once you've been given access so you can be added to the project.
3. Now you have access to the database. Log on to REDCap. On the welcome screen, open the HALT NTM project.
4. On the left hand side under Applications, open the File Repository. Download the HALT NTM cheat sheet.
5. Print a HALT NTM cheat sheet for each unique pair:
 - If there are two patients listed on your letter, you will have one unique pair.
 - If there are three patients listed on your letter, you will have three unique pairs.
 - If there are four patients listed on your letter, you will have six unique pairs.
 - This is because the date ranges are compared between two subjects and is unique for each pair.
6. Complete the first six lines on the HALT NTM cheat sheet for each unique pair. You will need to refer to it during pairing and data extraction.
7. Back in REDCap, on the left hand side under Data Collection, click Add / Edit Records. On the Add/Edit Records page, click on the button Add new record. You will be taken to the Record Home Page. There will be a NEW Study ID XXX-XX. Record that number (XXX-XX) on the HALT NTM cheat sheet. It is auto-generated by REDCap. You will need it later.
8. The first Form to complete is Demographics. Open the form by clicking on the circle under Demographics. Near the top of the form under the header **Pairs Survey** is a link to the "**Finding Pairs survey**." Click on the link. You will be taken to an interactive tool that will help you determine if this subject is "subject 1" or "subject 2" in this pairing.
9. Using the letter from NJH ADx and the HALT NTM cheat sheet, answer the questions. This will give you the pair number and subject number for the patients. Record those numbers on the HALT NTM cheat sheet. You may also choose to click Submit and then Download to get a printout of your survey responses for your record.

10. Back on the Demographic form, complete the questions for the first subject in the pair. Have the HALT NTM cheat sheet handy. You will use it to enter the Pair Number, Subject Number, culture dates, and isolate ID into REDCap. Enter as much data as you can. Once complete, click on Save & Exit Form button.
11. Repeat Steps 6-9 for the second subject in the pair.
12. Now that you have the demographics and some background information entered for both subjects in a pair, the next Form to complete is Compare. You can access it from the Record Status Dashboard **or** from Add/Edit Records listed under Data Collection on the left hand side.
13. Using the HALT NTM cheat sheet, answer “For this pairing, is this Subject 1 or Subject 2?” Depending on your answer, you will be asked to enter a date for the **OTHER PATIENT** in this pairing. Be sure to read the questions carefully and enter the correct date.
14. Once the date has been entered, a box will pop-up with the Extraction Date Range. Record this on the HALT NTM cheat sheet.
15. Now for the digging. In order to see if your pair of patients had any overlap, you will need to enter dates for Inpatient hospitalizations, Outpatient Clinic visits, and Research Unit visits. Only record visits that fall within the Extraction Date Range.
16. Keep digging! You’ve completed the extraction for the first subject in the pair. Now repeat Steps 12-15 for the second subject in the pair.
17. Once you have completed the Compare Form (all the date extractions) for a pair of subjects, you are ready to see if there is any overlap between these two patients. Click on “Compare Dates” on the left side under Project Bookmarks. You will be asked to enter the internal record id (**XXX-XX**) for the two subjects in the pair you are comparing.
18. Take a deep breath and click “Compare subjects.” The program will let you know if there is any overlap in dates for Inpatient, Clinic, and/or Research Visits. If there is, REDCap will mark those forms as **red circles** on the Record Status Dashboard. If there is no overlap, the circles will stay grey and you are done with this pair.
19. However, if you have **red circles** on the Record Status Dashboard, it is time to dig again. Clicking on a **red circle** will take you to an Overlap Form – there is one form for each location the program found date overlaps. The top of the form is uneditable, but you are able to see the Patient Name, Pair Number, Subject Number, and Date Range for the detailed data extraction. Use this information to complete the questions as best you can for each visit overlap (**red circle**). The more accurate you are able to be, the better the analysis can be.
20. Once done, change status to “Complete,” and click “Save & Exit”. The status color changes to **green** on the Record Status Dashboard. You are done.

Feel free to contact [name] or [name] for help along with way or if you have any comments on this user guide or the REDCap project.

[name]
[contact]
[contact]

[name]
[contact]
[contact]

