
In this study, we are unable to exclude NTM acquisition from direct patient-to-patient contact or via a common environmental source outside the healthcare setting. Evaluation of non-healthcare settings is beyond the scope of this project, but serves as a potential future area of investigation. There may also be a baseline frequency of patient overlap that is not related to transmission events in the healthcare setting that we expect to capture with evaluation of control pairs of subjects. Despite this small sample size, this preliminary data provides insight into the frequency and nature of patient overlap in the healthcare setting and reveals that among CF patients receiving healthcare in the same location, there are opportunities for close direct or indirect contact. In the setting of strict IP&C measures with single patient rooms, healthcare staff gowning and gloving, patients wearing masks, aggressive cleaning procedures between patients, and maintenance of patient-to-patient separation of 6 feet or more, direct and indirect patient overlap should be minimized. However, incidental or unanticipated contacts remain a risk. If patients in fact have no direct or indirect contact, *investigation of the healthcare environment is essential to eliminate a common healthcare-associated environmental source as the point of CF patient NTM acquisition*.

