When highly similar isolates are identified within an individual Care Center, a form letter entitled, CO-RDP NTM Isolate Results for CF Care Centers (**Appendix 1**), will be sent to each affected institution. The letter informs the Centers of highly similar NTM isolates among two or more patients within their Center. The letter will also extend the invitation to participate in the HALT NTM study. To put the study in context, we will provide a summary of cluster data available to date, the goals and methods of this study, as well as IRB documents. The invitation to participate in HALT NTM will initiate a simple enrollment process and recommend collaboration with the Center’s local IP&C team for investigation into a potential healthcare-associated transmission event. With enrollment, instructions will be provided on how to access the web-based HALT NTM investigation toolkit to facilitate a standardized healthcare-associated NTM investigation and a HALT NTM Toolkit User’s Guide will be provided (**Appendix 2**).

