4 STUDY DESIGN

4.1 Study Overview

PART A / Epidemiologic Investigation:

This study will retrospectively review and collect data from patients with CF and culture positive for an NTM isolate falling in a highly-related cluster, identified by the CO-RDP, within a single CF Care Center. Two control subjects will be identified by the CO-RDP for every subject falling within a cluster. Retrospective epidemiologic data collection and input into REDCap is detailed (**Appendix 1 and 2**). Up to 20 Care Centers will be offered enrollment.

PART B / Water Biofilm Collection:

This study will also collect and analyze water biofilms from a variety of water sources in the healthcare setting including sink faucets, showerheads, shower hoses, ice machines, drinking fountains, and decorative water features. Environmental sampling instructions are detailed (**Appendix 3**).

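### Abstractors work from the letter that identifies the clustered patients, and nothing requires equal searching for control pairs, which could bias room-level overlap away from the null

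*Protocol*

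**What the plan says.** **Disclosure comes first.** Protocol Section 2 describes the form letter that invites a Center to take part: "The letter informs the Centers of highly similar NTM isolates among two or more patients within their Center". The user guide in Appendix 2 opens by addressing a Center that holds a letter "saying you have patients at your center with a highly similar strain of NTM".

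**The letter is a tool of abstraction.** Step 5 counts pairs from it: "If there are two patients listed on your letter, you will have one unique pair". Step 9 assigns pair and subject numbers from it: "Using the letter from NJH ADx and the HALT NTM cheat sheet, answer the questions".

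**Site staff collect the exposure.** Section 16.1: "Study personnel at each site will enter data from the electronic medical record and CF Registry". Under Appendix 2, steps 14 to 18, REDCap displays the extraction window, staff type in the inpatient, clinic and research visits that fall inside it, and the program reports whether dates overlap. Where it flags an overlap, step 19 opens a detailed form: "Use this information to complete the questions as best you can for each visit overlap". That form displays the patient's name and the pair number.

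**Controls.** Section 4.1: "Two control subjects will be identified by the CO-RDP for every subject falling within a cluster". Section 1.2 gives the reason for studying control pairs: "There may also be a baseline frequency of patient overlap that is not related to transmission events". The user guide has no step for control pairs.

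**Use of the data.** Sections 15.1 and 15.3 compare proximity between pairs with similar strains and pairs with dissimilar strains, by t-tests and by linear and logistic regression.

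**The concern.** Proximity is the exposure, and strain similarity defines the groups. The person who searches for the exposure holds the document that identifies one of the groups. If a pair already suspected of transmission is searched harder than a control pair, more of its true overlap is found, and an association appears where none exists.

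The measure most exposed is the point instance, meaning the same physical room, because it depends on how far the abstractor traces rooms and times. It is also the overlap evidence closest to transmission. Analysis cannot recover rooms that were never looked up for controls, so this is a matter of design and conduct, not one to leave to the SAP.

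**Working it through.** **Figures in the plan.** The protocol gives no overlap rate, number of pairs, alpha or power for this comparison, so there is no planned figure to reproduce. The pair counts in Appendix 2, step 5 (2, 3 and 4 patients give 1, 3 and 6 pairs) equal n(n−1)/2 and are correct.

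**Where discretion enters, step by step**

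| Step | Who decides | Room for differential effort |
|---|---|---|
| Extraction window | REDCap, from entered culture dates | Little |
| Finding and entering visits | Site staff, by hand | Some |
| Date overlap yes/no | Program | None beyond the entered dates |
| Room and time detail | Site staff, no completeness standard | Most |

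**Illustration 1: odds ratio when there is no true association.** Let p be the true overlap in both groups, and a and b the share found in cluster and control pairs. All three are assumptions.

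OR = [pa/(1−pa)] / [pb/(1−pb)], with p = 0.30:

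- a = 0.90, b = 0.80: (0.27/0.73)/(0.24/0.76) = 0.370/0.316 = 1.17
- a = 0.90, b = 0.70: (0.27/0.73)/(0.21/0.79) = 0.370/0.266 = 1.39
- a = 0.95, b = 0.60: (0.285/0.715)/(0.18/0.82) = 0.399/0.220 = 1.82

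**Illustration 2: false-positive rate.** Assume p = 0.50, a = 0.95 and b = 0.75, so the observed shares are p1 = 0.475 and p2 = 0.375 and the OR is 0.905/0.600 = 1.51. Assume a pooled two-proportion test at two-sided 0.05 with two control pairs per cluster pair. With d = p1 − p2, SE0 the pooled and SE1 the unpooled standard error:

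rate = Φ[(d − 1.96·SE0)/SE1] + Φ[(−d − 1.96·SE0)/SE1]

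For 40 cluster and 80 control pairs, the pooled share is (19 + 30)/120 = 0.408, SE0 = 0.0952 and SE1 = 0.0957. The rate is Φ(−0.90) + Φ(−2.99) = 0.183 + 0.001 = 0.184.

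| Cluster pairs | 20 | 40 | 60 | 100 |
|---|---|---|---|---|
| False-positive rate | 12% | 18% | 25% | 38% |

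Holding cluster capture at 95% and varying true overlap from 30% to 70% and control capture from 85% to 65%, the OR runs from 1.16 to 2.38. The false-positive rate runs from 6% to 33% with 20 cluster pairs and from 9% to 94% with 100. With equal capture (90% in each group) the OR is 1.00 and the rate 5.0% throughout.

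**Limits of the arithmetic.** Pairs that share a patient are not independent, so these rates are only illustrative. The calculation covers yes/no overlap, not the t-tests or linear models on degree of proximity. It also assumes that control pairs enter the comparison, as Section 1.2 intends. Section 15.1.1 bases all analyses on clustered patients and needs reconciling with that.

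**The case against.** Four points can be made against the concern.

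*REDCap limits discretion.* It sets the window, decides date overlap, and opens detailed forms only where it flags one. Sections 16.1 and 16.2 add investigator verification, validation checks and an audit trail. This stands for visit-date overlap, apart from visits that nobody entered. It does not reach room-level detail: none of these checks masks anyone or compares completeness between groups.

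*The bias is not shown.* This stands. A reader might infer that the plan does bias the result away from the null. The documents support only that it could: they give no capture rates, and the 35-point gap behind the 1.82 is an assumption.

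*The handling of controls is not fully visible.* This stands in part. A reader might infer that controls arrive separately from the cluster letter, or that contact with staff is traced. The protocol says only that the CO-RDP identifies the controls, and Appendix 2 does not describe tracing staff. The letter in Appendix 1 was not available for checking, so it may list controls too.

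*The Center must know its cluster.* This stands. The letter precedes enrollment and recommends involving local infection control, so cluster status cannot be withheld from the Center. What can change is what the individual abstractor works from. Even then, recorded species could reveal that a pair is not clustered unless controls share the species, which the protocol does not state.

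**Conclusion.** The concern holds as a risk in the design. Cluster status is a working input to abstraction, detail within an overlap depends on effort, and no visible step secures equal ascertainment for the pairs that supply the baseline. The comparison of similar with dissimilar pairs could be biased away from the null, chiefly for point-instance overlap and less for date overlap.

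The size cannot be derived from the protocol. At 30% true overlap, the assumed capture rates give odds ratios of 1.17 to 1.82 against a truth of 1.0. The documents do not show that the bias occurs, and they do not support reading visit overlap as wholly discretionary. The change is worth making because it is cheap and must precede abstraction: an abstractor who already knows cluster status cannot be masked later.

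**What to change.** In Section 4.1 and Appendix 2:

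1. The CO-RDP issues one randomly ordered list of pre-numbered cluster and control pairs without cluster labels. It carries the culture dates and coded isolate IDs that the forms need.
2. The same forms and the same extraction-window rule apply to every pair.
3. The Center still receives its letter. Where existing staffing allows, the abstractor works from the list and not from the letter.
4. Room and time detail is required on the same terms for every program-flagged overlap in both groups, with an explicit entry for not available. Pairs without a flagged overlap still stop at step 18.
5. Add one REDCap field: abstractor aware of cluster status (Y/N).
6. Report missing room and time fields by group. Repeat the main analysis on program-determined date overlap alone and, if numbers allow, in records from unaware abstractors.

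**Cost.** List preparation at the CO-RDP, a revision of Appendix 2 so that the pairing steps run from the list, and one added field. No extra staff are assumed. Masking will be incomplete at small Centers, which the awareness field will show, and the analysis of unaware records may be sparse.
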